### 4.5.3 Allocation/Randomization of Subjects to Treatment

Prior to dosing on Day 1, subjects will be assigned a randomization number in accordance with the randomization code generated by PAREXEL using PROC PLAN method of SAS. The assigned randomization number will determine the treatment the subject receives.

Once a randomization number has been allocated to one subject, it may not be assigned to another subject. If subjects withdraw prematurely from the study and are replaced under the direction of the Sponsor, a replacement randomization number will be assigned. A replacement

randomization code will be generated such that replacement subjects are assigned to the same treatment as the discontinued subjects.

## 5 STUDY DRUG

### 5.1 Identity

The Sponsor will provide the Investigator with adequate quantities of the study drugs, as described in Table 5-1.

**Table 5-1: Identity of the Study Drugs**

Study Drug	Formulation	Strength	Route	Manufacturer
KM-819	White circular tablet	10 mg	Oral	HanAll BioPharma Co., Ltd.
		100 mg		
Placebo	White circular tablet	0 mg	Oral	HanAll BioPharma Co., Ltd.

The composition of each KM-819 tablet is presented below (see Table 5-2):

**Table 5-2: Composition of Each Study Drug Tablet**

Ingredient	Function	Quantity		
		KM-819 10 mg strength	KM-819 100 mg strength	Placebo
KM-819	Main ingredient	10 mg	100 mg	0 mg
Crystallized cellulose	Diluting agent	245 mg	157 mg	216 mg
Pre-gelatinized starch	Diluting agent	44 mg	44 mg	55 mg
Povidone	Bonding agent	24 mg	22 mg	27 mg
Crosscarmellose sodium	Disintegrating agent	11 mg	11 mg	29 mg
Colloidal silicone dioxide	Fluidizing agent	15 mg	15 mg	19 mg
Stearic magnesium	Lubricant Agent	11 mg	11 mg	14 mg

### 5.2 Administration

Study drug (KM-819 or placebo) will be administered orally at the study center.

The study drug should be administered with approximately 240 mL of water (room temperature), after an overnight fasting for a minimum of 8 hours. No food should be allowed for at least 4 hours postdose. Water will be allowed as desired except for 1 hour before and after drug administration.

For Part B (MAD) study, on Day 2 to Day 6, the study drug should be administered with approximately 240 mL of water (room temperature), after an overnight fasting for a minimum of 8 hours. No food should be allowed for at least 2 hours postdose. Water will be allowed as desired except for 1 hour before and 2 hours after drug administration.

Each dispensing of study drug will be documented in the eCRF.

### **5.3 Rationale for Selection of Starting Dose**

The FDA Guidance “Estimating the Safe Starting Dose in Clinical Trials for Therapeutics in Adult Healthy Volunteers” and allometric scaling modeling and simulation were used for the initial calculation of the starting human dose in this study. Based on the FDA Guidance document and the 4-week rat toxicology study NOAEL of 500 mg/kg/day, the human equivalent dose (HED) is estimated to be 5600 mg for a 70 kg human subject. A 10-fold safety factor is applied to the HED, resulting in an estimated Maximum Recommended Starting Dose (MRSD) was 560 mg per person for a 70 kg person. In addition to the FDA Guidance method, an allometric scaling method was used to predict human PK. The human PK parameters were predicted as followed: CL= 2.93 L/h, V = 39.2 L, and half-life =9.27 hours. Using these predicted human PK parameters, simulation was conducted based on the assumption that human PK behaves with one compartment model with first order absorption and first order elimination rate and the bioavailability was assumed to be 35% (mean F from animal data).

Based on simulated human PK profile and animal efficacy data, a lower dose was chosen for the starting dose.

The first-in-human Phase 1 single ascending dose study will have an initial starting dose of 10 mg, which is x56-fold below the estimated MRSD derived from the rat NOAEL.

### **5.4 Packaging, Labeling and Storage**

Study drug will be packaged by Kainos Medicine, Inc. according to all local legal requirements. Study drug will be labeled in accordance with applicable regulatory requirements.

All study drug supplies must be stored in accordance with the manufacturer’s instructions (stored at a temperature of 1–30°C). Until dispensed to the subjects, the study drug will be stored in a securely locked area, accessible to authorized personnel only.

### **5.5 Blinding and Breaking the Blind**

The study will be performed in a double-blind manner. All study drugs will be supplied in identical tablets and will be similar in color, smell, taste, and appearance, thereby enabling double-blind conditions.

For this study, the bioanalyst will be unblinded for dose escalation PK analysis.

For each randomized subject, an individual emergency (randomization) code break envelope will be stored in a secure location with access by designated staff members to open in the event of a medical emergency requiring knowledge of a subject’s treatment assignment.

The blind must only be broken following discussion on a case-by-case basis, at the discretion of the Sponsor/PI.

If the blind is broken, the date, time, and reason must be recorded in the subject’s eCRF, and any associated AE report.

If an emergency unblinding becomes necessary, the Investigator should notify the Sponsor/PI, if possible, prior to unblinding. The Investigator is responsible for opening the specified envelope, in the presence of a witness, both of whom must sign and date the envelope.

All envelopes, whether sealed or opened, must be returned to PAREXEL at the end of the study.

Serious unexpected suspected adverse reactions (SUSARs), which are subject to expedited reporting, should be unblinded before submission to the Regulatory Authorities.

The overall randomization code will be broken only for reporting purposes. This will occur once all final clinical data have been entered into the database and all data queries have been resolved, and the assignment of subjects to the analysis sets has been completed.

## **5.6 Drug Accountability**

The Investigator is responsible for maintaining accurate study drug accountability records throughout the study.

The Investigator is responsible for returning all unused or partially used study drug to the Sponsor and must verify that all unused or partially used drug supplies have been returned by the subject and that no remaining supplies are in the Investigator's possession.

## **5.7 Compliance**

Dosing will take place at the study center. The dose and schedule of study drugs administered to each subject will be recorded on the appropriate form. The administration of KM-819 (or placebo) will be supervised by the Investigator or a medically qualified staff member to ensure treatment compliance. After medication intake, the subject's hands and mouth will be inspected to ensure that the tablets have been swallowed completely. Treatment compliance should be monitored closely and any deviation in compliance should be reported to the Sponsor.

## **5.8 Previous and Concomitant Medications**

Any medication that the subject takes other than the study drug, including herbal and other non-traditional remedies, is considered a concomitant medication. All concomitant medications must be recorded in the eCRF. The following information must be recorded in the eCRF for each concomitant medication: generic name, route of administration, start date, stop date, dosage, and indication. Any changes in the dosage or regimen of a concomitant medication must be recorded in the eCRF.

At Screening, subjects will be asked what medications they have taken during the last 3 months. At each subsequent study visit, subjects will be asked what concomitant medications they are currently taking.

In all study cohorts, no concomitant medications will be allowed, with the exception of acetaminophen (up to 2000 mg/day) (as per Exclusion Criteria 11).

## **5.9 Restrictions during the Study**

- Alcohol use is prohibited from 48 hours prior to check-in and throughout the duration of the study.
- Caffeine-containing products (coffee, tea, chocolate) are prohibited from 48 hours prior to check-in and throughout the duration of the study (except for ambulatory period before Follow-up Visit).
- Grapefruit, Seville oranges, star fruit, or any products containing these items are prohibited within 48 hours days prior to dosing and throughout the duration of the study.

- Subjects will not be allowed to consume food or drinks, which may interact with circulatory, gastrointestinal, liver or renal function (e.g. alcohol, caffeine, or caffeine containing products, or grapefruit juice) throughout the duration of the study. Subjects will be served normal balanced caloric drinks and meals at standardized times during their stay in the study center. Total daily caloric intake will preferably not exceed normal daily limits (2500 kcal).
- Smoking and other nicotine-containing products are prohibited within 6 months prior to Screening and throughout the duration of the study.
- Strenuous activity is prohibited from 48 hours prior to check-in until discharge. After discharge, mild physical activity can be resumed, but strenuous physical activity is prohibited until the Follow-up Visit.
- Blood donation is prohibited throughout the duration of the study.

## 6 VARIABLES AND METHODS OF ASSESSMENT

### 6.1 Pharmacokinetics and Pharmacodynamics Assessment

#### 6.1.1 *Pharmacokinetics Assessment*

Plasma and CSF samples for PK analysis of KM-819 will occur at the time points relative to dosing described on Table 7-1 and Table 7-2.

The actual date and time of PK blood and CSF samples collection will be captured in the eCRFs. Blood and CSF collection, handling, storage, and shipping details will be addressed in the Laboratory Manual.

#### 6.1.2 *Pharmacodynamic Assessment*

Scales (Bond and Lader VAS, POMS, and K-WAIS-IV) and C-SSRS will be evaluated at the time points described on Table 7-1 and Table 7-2.

CSF and plasma samples for MAD PD analysis will occur at the time points described on Table 7-1 and Table 7-2.

### 6.2 Pharmacokinetic Variables

#### 6.2.1 *KM-819 Pharmacokinetic Blood Sampling*

Blood (approximately 6 mL) will be taken by venipuncture or cannulation of a forearm vein(s) and collected into anticoagulant EDTA K2 tubes. Blood will be processed for plasma by centrifuging at 4°C, 3000 rpm for 10 min. The obtained plasma will be transferred into 3 polypropylene tubes (1.5 mL) with a volume of 0.8 mL, respectively. The tubes will be immediately stored at -70°C freezer. Two aliquots of plasma samples will be transferred to Bioinfra Co., Ltd and be analyzed by a validated method for the concentration of KM-819 (Parts A and B); one aliquot will be stored in study center as a back-up until completion of the clinical study report (CSR).

The PK parameters listed in Section 3.2.2 will be calculated from the plasma concentration-actual time profiles. The non-compartmental analysis will be performed using Phoenix® WinNonlin® Software Version 6.3 or higher (Certara, L.P., [name]).

The total volume of PK blood drawn from each subject will be approximately 72 mL in Part A SAD and 144 mL in Part B MAD.

#### 6.2.2 *KM-819 Urine Sampling*

Urine samples for possible analysis of KM-819 and qualitative analysis of any metabolites will be collected at intervals relative to study drug dosing as detailed in the Schedule of Procedures (Table 7-1 and Table 7-2). Within 60 minutes prior to dosing on Day 1, each subject will be instructed to void their bladder and no more than 20 mL of this urine sample will be retained as a control. Urine collection will begin immediately following dose administration. A 0 to 24 hour urine collection will be made for each subject and the volume will be recorded. After sampling, urine samples will be transferred into 3 polypropylene tubes (1.5 mL) with a volume of 1 mL, respectively. The tubes will be immediately stored at -70°C freezer.

At the completion of Part A, the urine sample collections obtained from the highest single dose cohort from Part A will be shipped to the analytical site and analysed for KM-819 metabolites. Two aliquots of urine samples will be transferred to Bioinfra Co., Ltd and 1 aliquot will be stored in study center as a back-up until completion of the CSR. Results will be reported under a separate protocol, if metabolite profiling was completed. All other urine samples from earlier periods will be defrosted and discarded by the Clinical Research Unit.

### **6.2.3 KM-819 Pharmacokinetic CSF Sampling**

CSF (approximately 2 mL) will be taken by lumbar puncture between the 3rd and 4th lumbar vertebrae. CSF samples will be transferred into 3 polypropylene tubes (1.5 mL) with a volume of 0.5 mL, respectively. The tubes will be immediately stored at -70°C freezer. Two aliquots of CSF samples will be transferred to Bioinfra Co., Ltd and be analyzed by a validated method for the concentration of KM-819 (Part B only); one aliquot will be stored in study center as a back-up until completion of the CSR.

## **6.3 Pharmacodynamic Variables**

### **6.3.1 Scales**

#### **6.3.1.1 Bond and Lader VAS**

The Bond-Lader VAS will be used to rate subjects' feelings in terms of 16 dimensions. The dimensions will be presented as 100 mm lines, the 2 extremes of the emotion (i.e., 'alert' and 'drowsy') written at each end, and subjects will be asked to record their current state on each line.

The Bond-Lader VAS will be analyzed using 3 factor scores: alertness, contentedness, and calmness. Calculation of these 3 scores is based on the main factors resulting from statistical factor analysis. A high score indicates impairment.

1. Alertness (9 subscales):  $[Q1 + Q3 + (100 - Q4) + Q5 + (100 - Q6) + (100 - Q9) + Q11 + (100 - Q12) + Q15] / 9$
2. Contentedness (5 subscales):  $[Q7 + (100 - Q8) + Q13 + (100 - Q14) + (100 - Q16)] / 5$
3. Calmness (2 subscales):  $[Q2 + (100 - Q10)] / 2$

Ratings will be performed at the time points detailed in Schedule of Procedures (Table 7-1 and Table 7-2).

#### **6.3.1.2 Profile of Mood States**

POMS will be used to describe subjects' feelings with a questionnaire containing 65 words/statements. Feelings will be scored using different statement: "Not at All", "A Little", "Moderately", "Quite a lot", and "Extremely".

Assessments will be performed at the time points detailed in Schedule of Procedures (Table 7-1 and Table 7-2).

#### **6.3.1.3 Korean Wechsler Adult Intelligence Scale-IV**

The K-WAIS-IV consists of an assessment of the cognitive ability using a core battery of 10 unique subtests (Block Design, Similarities, Digit Span, Matrix Reasoning, Vocabulary, Arithmetic, Symbol Search, Visual Puzzles, Information, and Coding) that focus on four specific

domains of intelligence: verbal comprehension, perceptual reasoning, working memory, and processing speed.

Only the Coding subtest will be assessed at the time points detailed in Schedule of Procedures (Table 7-1 and Table 7-2).

### **6.3.2 *Columbia Suicide Severity Rating Scale***

The C-SSRS is a scale that captures the occurrence, severity and frequency of suicide-related thoughts and behaviors during the assessment period. The scale includes suggested questions to solicit the type of information needed to determine if a suicide-related thought or behavior occurred. The C-SSRS must be administered by appropriately trained site personnel. The C-SSRS will be administered at the times specified in Schedule of Procedures (Table 7-1 and Table 7-2).

### **6.3.3 *KM-819 Pharmacodynamic Blood Sampling***

Blood (approximately 3 mL) will be taken by venipuncture or cannulation of a forearm vein(s) and collected into appropriate collection tubes (only on Part B). The PD parameters listed in Section 3.2.2 will be calculated.

The total volume of PD blood drawn from each subject will be approximately 6 mL.

### **6.3.4 *KM-819 Pharmacodynamic CSF Sampling***

CSF (approximately 1.5 mL) will be taken by lumbar puncture between the 3rd and 4th lumbar vertebrae (only on Part B). The PD parameters listed in Section 3.2.2 will be calculated.

## **6.4 Safety Variables**

### **6.4.1 *Adverse Events***

#### **6.4.1.1 *Collection of Adverse Events***

It is responsibility of the Investigator to collect all AEs (both serious and non-serious) derived by spontaneous, unsolicited reports of subjects, by observation and by routine open questionings e.g., "How have you felt since I last saw you?"

#### **6.4.1.2 *Definitions***

An AE is any untoward medical-occurrence that occurs in a subject or clinical investigation subject administered a pharmaceutical product, and which does not necessarily have to have a causal relationship with this treatment. An AE can therefore be any unfavorable and unintended sign (including abnormal laboratory finding), symptom, or disease temporally associated with the use of an investigational product, whether or not considered related to the product.

All AEs, including intercurrent illnesses, occurring during the study will be documented in the eCRF. Concomitant illnesses, which existed before entry into the study, will not be considered AEs unless they worsen during the treatment period. All AEs, regardless of the source of identification (e.g., physical examination, laboratory assessment, ECG, reported by subject), must be documented.

Pre-existing conditions will be recorded in the eCRF on the medical history or appropriate page.

A TEAE will be defined as an AE that begins or that worsens in severity after at least one dose of study drug has been administered.

#### *6.4.1.3 Assessment of Adverse Events*

Each AE will be assessed by the Investigator with regard to the following categories.

##### *6.4.1.3.1 Seriousness*

A serious AE (SAE) is defined as any untoward medical occurrence that at any dose:

- Results in death;
- Is life-threatening;  
This means that the subject is at risk of death at the time of the event; it does not mean that the event hypothetically might have caused death if it were more severe;
- Requires inpatient hospitalization or prolongation of existing hospitalization;
- Results in persistent or significant disability or incapacity;
- Is a congenital anomaly or birth defect;
- Is an important medical event(s) that may not be immediately life-threatening or result in death or hospitalization but that may jeopardize the subject or require intervention to prevent one of the above outcomes. Examples of such events are intensive treatment in an emergency room or at home for allergic bronchospasm; blood dyscrasias or convulsions that do not result in hospitalization; or development of drug dependency or drug abuse.

Medical and scientific judgment should be exercised in deciding whether a case is serious and whether expedited reporting is appropriate.

##### *6.4.1.3.2 Intensity*

The intensity of each AE must be assessed by the Investigator using one of the following categories, and recorded in the eCRF:

- Mild: The AE was transient and easily tolerated by the subject.
- Moderate: The AE caused discomfort and interferes with the subject's general condition.
- Severe: The AE caused considerable interference with the subject's general condition and may have been incapacitating.

##### *6.4.1.3.3 Causality*

The Investigator will assess the causality / relationship between the study drug and the AE and record that assessment in the eCRF.

The most likely cause of an SAE (e.g., disease under treatment, concomitant disease, concomitant medication, other) will be indicated on eCRF with details of the concomitant disease or medication or other cause.

The causal relationship of the AE to study drug will be described as one of the following terms:

**Table 6-1: Causal Relationship of Adverse Event to Study Drug**

Causal relationship	Description
Definite	A clinical event with a plausible time relationship to drug administration and which cannot be explained by concurrent disease or other drugs or chemicals. Response to withdrawal plausible (pharmacologically, pathologically), Event definitive pharmacologically or phenomenologically (i.e., an objective and specific medical disorder or a recognized pharmacological phenomenon), Rechallenge satisfactory, if necessary.
Probable	A clinical event with a reasonable time relationship to drug administration is unlikely to be attributed to concurrent disease or other drugs or chemicals. Response to withdrawal clinically reasonable (Rechallenge not required).
Possible	A clinical event with a reasonable time relationship to drug administration, but which could also be explained by concurrent disease or other drugs or chemicals.
Unlikely	A clinical event whose time relationship to drug administration makes a causal connection improbable, which could be plausibly explained by underlying disease or other drugs or chemicals.
Not related	A clinical event with no time relationship to drug administration, or with no causal relationship to drug administration (e.g., definitely induced by the clinical conditions of the subject or by the test procedures/requirements or by external events which are not associated with study treatments).
Unassessable	A clinical event with insufficient or contradictory information to permit assessment and identification of the cause.

The causal relationship of definite, probable, possible and unassessable will be considered as related to study drug.

#### 6.4.1.3.4 Adverse Events of Interest

An adverse event of interest (AEI) is an event which, in the evaluation of safety, has a special focus. An AEI is an AE (SAE or non-serious AE) which fulfils below defined AEI criteria:

- Potential Hy's law cases

Potential Hy's law, defined as  $\geq 3 \times$  ULN ALT with co-existing  $\geq 2 \times$  ULN bilirubin in the absence of  $\geq 2 \times$  ULN ALP, with no alternative explanation for the biochemical abnormality, must always be reported as an AE of interest (i.e., without waiting for any additional etiologic investigations to have been concluded). Follow-up information should then be reported if an alternative etiology is identified during investigation and monitoring of the subject.

AEI should be reported to the Sponsor/PAREXEL immediately (within 24 hours of the site being aware of the event).

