### **3.5 Stopping Criteria for Dose Escalation**

Dosing will be stopped if 1 (or more) of the following apply. Depending on the nature of the AEs, it could be decided to investigate a lower dose level (intermediate between the current and the prior one) in the next group.

1. If 1 or more subjects experiences a study drug-related serious adverse event (SAE), unblinding of the subject(s) will be done. If the subject(s) was (were) on active treatment, dosing will be stopped.
2. If 2 subjects in 1 dose group show the following findings in 2 consecutive postdose measurements within 24 hours and if unblinding reveals that both subjects received active treatment, dosing will be stopped:
  - a. ALT or AST  $\geq 3 \times$  upper limit of normal (ULN) or,
  - b. ALT or AST  $\geq 2 \times$  ULN and ALT or AST  $\geq 5 \times$  baseline value or,
  - c. TBIL  $\geq 2 \times$  ULN
3. If 2 or more subjects in 1 cohort experience AEs of severe intensity or 4 or more subjects in 1 cohort experience AEs of moderate intensity, which are considered by the PI and/or Sponsor to be possibly or probably related to the investigational product, and of clinical concern, and if unblinding reveals that these subjects received active treatment, dosing will be stopped.

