### ***3.5.1 PK stopping criteria***

Due to the liver damage (higher ALT, ALP, GGT, and enlargement in common bile duct in liver) reported in one male dog following multiple dosing at 2000 mg/kg for 7 days, and NOAEL in male and female beagle dog at 1000 mg/kg/day for 14 days, the decision to escalate to the next planned dose will be based on review of PK exposure data from previous dose cohort(s). This will involve use of best available modeling practices of the observed AUC (i.e.,  $AUC_{\text{tau}}$  or  $AUC_{0-\infty}$ ) and  $C_{\text{max}}$  from each dose, resulting in a predictive distribution of AUC and  $C_{\text{max}}$  at higher dose levels. If predicted mean AUC and  $C_{\text{max}}$  for the next dose level is higher than 41.3 ug.h/mL and 9.3 ug/mL, respectively, then the dose escalation will stop and the Sponsor and PI will need to review the totality of data, including safety and PK before make any dose escalation decision. This PK stopping criteria are based on dog 2-Week study NOAEL exposure at 1000 mg/kg/day (the most conservative species and gender).

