#### 4.3 Subject Withdrawal and Replacement

A subject may withdraw from the study at any time without penalty and for any reason without prejudice to his/her future medical care. Participation of subjects may also be discontinued based on the medical judgment of the PI in conjunction with the Sponsor for any of the following reasons:

- ECG abnormalities:  
Any increases in QTcF > 500 msec or increase > 60 msec from baseline as confirmed with 3 consecutive ECGs taken within 5 minutes, with at least a 1-minute interval.
- Suicidality:  
Any suicide attempt or any recent suicidal ideation (a level of 4 or 5) since the last assessment, or a significant risk to commit suicide, as judged by the PI using the C-SSRS.
- Liver Safety Monitoring:  
Please refer to Stopping Criteria No. [2](#).
- After enrolment, the subject is found to violate the inclusion and/or exclusion criteria
- AE(s)
- Subject lost to follow-up
- Major protocol violation
- Use of prohibited medications mentioned in Section [5.8](#)
- The Investigator may, after discussion with the subject, withdraw the subject due to any serious safety concerns
- The study is terminated prematurely
- Other

In all cases, the reason(s) for withdrawal, and the primary reason, must be recorded on the electronic case report form (eCRF). Subjects who are withdrawn will have an Early Discontinuation (ED) Visit per the Schedules of Assessments (see Table [7-1](#) and Table [7-2](#)).

A subject may also be withdrawn from study by the Sponsor, Regulatory Authorities, or IECs/IRBs.

Subjects will also be withdrawn if the entire study is terminated prematurely as described in Section [9.10](#).

Withdrawn subjects may be replaced at the discretion of the Sponsor with agreement of the Investigator. Subjects who are discontinued because of treatment-emergent AE (TEAE) or possible toxic effects of the drug will not be replaced.

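### The 24-hour report for a potential Hy's law case counts ALT only, whereas the liver stopping criterion counts ALT or AST at the same 3 × ULN level

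*Protocol*

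**What the plan says.** Protocol section 6.4.1.3.4 defines a single AEI, the potential Hy's law case. It needs ≥ 3 × "ULN ALT with co-existing" ≥ 2 × "ULN bilirubin in the absence of" ALP ≥ 2 × ULN. The definition continues: "with no alternative explanation for the biochemical abnormality, must always be reported as an AE of interest". The site is told not to wait for etiologic work-up, and to send follow-up information if another cause is found. The clock is set by the sentence "AEI should be reported to the Sponsor/PAREXEL immediately (within 24 hours of the site being aware of the event".

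Section 3.5, criterion 2 (repeated in the synopsis) is the group-level liver rule. It opens "If 2 subjects in 1 dose group show the following findings in 2 consecutive postdose measurements within 24 hours" and continues "if unblinding reveals that both subjects received active treatment, dosing will be stopped". Its three limbs are:

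- 2a: ALT or AST ≥ 3 × ULN
- 2b: ALT or AST ≥ 2 × ULN and ≥ 5 × baseline
- 2c: total bilirubin ≥ 2 × ULN

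Section 4.3, on individual withdrawal, sets no liver threshold of its own. Its liver item reads "Please refer to Stopping Criteria No" 2.

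**The concern.** The protocol treats AST as a liver marker on a par with ALT almost everywhere: in exclusion criterion 3, in the liver-enzyme panel of Table 6-2 and in criterion 2. The one place where AST drops out is the definition that starts the 24-hour AEI clock. The threshold is the same 3 × ULN, and nothing in the protocol explains the change.

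What is at stake is early notice of a single case. This is a first-in-human study, and liver injury is the toxicity that the protocol singles out. Section 3.5.1 introduces the exposure limits with the words "Due to the liver damage (higher ALT, ALP, GGT, and enlargement in common bile duct in liver) reported in one male dog". A lone subject whose aminotransferase rise is carried by AST, with raised bilirubin, can cross the protocol's own liver levels without prompt notice to the sponsor being required.

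A smaller point sits in the same sentence. The reference to there being no alternative explanation could be taken by a site as a condition to check before reporting, although the rest of the paragraph points the other way.

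**Working it through.** The documents state no figure on this point, so there is none to reproduce. The check applies the two rules to test profiles. The thresholds come from sections 6.4.1.3.4 and 3.5. The profiles are assumed for illustration.

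Rules, in multiples of ULN:

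- AEI as written: ALT ≥ 3 and bilirubin ≥ 2 and not ALP ≥ 2.
- Criterion 2 thresholds, numeric part only: 2a is met if the larger of ALT and AST is ≥ 3; 2c is met if bilirubin is ≥ 2. Limb 2b is not needed for these profiles.
- AEI with criterion 2's enzyme wording: the larger of ALT and AST ≥ 3 and bilirubin ≥ 2 and not ALP ≥ 2.

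| Profile | ALT | AST | Bilirubin | ALP | AEI as written | Crosses 2a and 2c levels | AEI with the same enzyme wording |
|---|---|---|---|---|---|---|---|
| AST-led, ALT below 3 | 2.5 | 4 | 2.5 | 1.2 | No | Yes | Yes |
| AST-led, ALT also ≥ 3 | 3.2 | 5 | 2.5 | 1.2 | Yes | Yes | Yes |
| ALT-led | 4 | 2 | 2.5 | 1.2 | Yes | Yes | Yes |
| AST-led, ALP ≥ 2 | 2.5 | 4 | 2.5 | 2.1 | No | Yes | No |

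Only the first profile changes. The gap is therefore exactly AST ≥ 3, ALT < 3, bilirubin ≥ 2 and ALP < 2 × ULN, in an event not judged serious.

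Next, does another provision require a report for that subject within 24 hours?

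- Criterion 2 does not act for one subject. It needs two subjects in a dose group, two consecutive measurements within 24 hours, and active treatment in both. This is equally so for a lone ALT-led case.
- Section 4.3 points back to criterion 2. Withdrawal on medical judgment is possible, but it carries no reporting clock.
- Section 6.4.2 has clinically relevant laboratory changes recorded as AEs, again without a 24-hour clock.
- Section 6.4.1.5 requires a 24-hour report if the event is an SAE. That depends on a seriousness judgment, for example as an important medical event under 6.4.1.3.1.
- SAP sections 6.3.15.1 and 6.3.15.2 plan AE tables, abnormal-value listings and shift tables test by test. There is no AEI output and no combined aminotransferase and bilirubin display.

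Finally, an illustration of why the single-subject route matters. With 6 subjects on KM-819 in a cohort and an assumed per-subject risk p of a qualifying liver finding, P(exactly 1) = 6p(1 − p)^5 and P(2 or more) = 1 − (1 − p)^6 − P(exactly 1).

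- p = 2%: 10.8% against 0.6%
- p = 5%: 6 × 0.05 × 0.95^5 = 23.2% against 3.3%
- p = 10%: 35.4% against 11.4%
- p = 20%: 39.3% against 34.5%

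At each of these assumed risks, a lone case is likelier than two or more. The values of p are not in the documents, and the figures do not measure how often the AST gap would arise.

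**The case against.** The two rules do different jobs. One stops group dosing and the other speeds up a report, and nothing in the documents says that they must share an enzyme definition. AST can rise for non-hepatic reasons, and the dog finding names ALT, ALP and GGT but not AST. Other safeguards exist: the SAE route with its 24-hour report, stopping criterion 1 for a single drug-related SAE on active treatment, withdrawal on medical judgment, and review of safety data by the investigator and sponsor after each cohort (section 3.3).

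Much of this stands. It shows that the mismatch is a design choice with backstops and not a contradiction that disables safety monitoring. It does not supply a reason for dropping AST from the reporting trigger, and the protocol gives none. Apart from the SAE route, none of the safeguards is a 24-hour report.

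A reader might infer four stronger things, which the documents do not support:

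- That the enzyme wording silences the two-subject rule. It does not; the count of subjects does.
- That one such laboratory record satisfies criterion 2. It can only cross the numeric levels, because criterion 2 needs two consecutive measurements.
- That the AEI is the only liver signal open to a single subject. The SAE route is another.
- That the definition defeats itself, because no case could be known to lack another cause when the report is due. The same paragraph says to report without waiting and to send any other cause as follow-up, so the intent is clear and only the wording could be tidier.

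**Conclusion.** The concern holds in a limited form. The AEI definition counts ALT only, criterion 2 counts ALT or AST at the same level, and the difference is unexplained. The consequence is one missed 24-hour AEI report for a lone, non-serious, AST-led case with ALT below 3 × ULN, bilirubin at or above 2 × ULN and ALP below 2 × ULN. No stopping decision is affected.

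The frequency cannot be estimated. The documents give no joint distribution of ALT, AST, bilirubin and ALP, so any percentage of missed cases would rest wholly on assumption. The planned exposure is 6 cohorts × 6 = 36 subjects on KM-819 in Part A and 5 × 6 = 30 in Part B, 66 in all, before any replacements. Exclusion criterion 3 also screens them for liver enzymes and bilirubin above ULN. The number of such cases is likely to be very small. The change is worth considering because it is cheap and concerns the toxicity that the protocol itself names, not because a large effect has been shown.

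**What to change.** Reconcile section 6.4.1.3.4 with criterion 2 in section 3.5 and the synopsis, so that the 24-hour reporting definition and criterion 2 use the same aminotransferase wording. The edit belongs in the reporting definition. Criterion 2, the withdrawal rules and all dosing and stopping rules stay as they are.

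In the same edit, state that whether another explanation exists is settled in the follow-up report and does not delay the first one, as the paragraph already intends.

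The cost is a sentence or two in the protocol. ALT, AST, bilirubin and ALP are already in the Table 6-2 panel, so no new sample or data field is needed. The downside is an occasional extra AEI report for an AST rise that proves not to be hepatic.
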